### **Funding**

Vancouver Coastal Health Research Institute & National Spasmodic Dysphonia Association

## **Brief Summary**

Laryngeal Dystonia (LD, also known as spasmodic dysphonia) is a focal, action-specific movement disorder with prominent effects on speech (1-2). Patients with LD lose their ability to speak due to involuntary contractions of their laryngeal muscles. As a result, LD tremendously affects an individual's quality of life by limiting their ability to communicate effectively.

The current standard of care for SD involves botulinum toxin (BTX) injections into the laryngeal muscles. BTX causes a weakness in the injected muscles thereby lessening the spasms (7). The primary neurological problem is not changed but weakening the muscles temporarily diminishes the symptoms. However, BTX therapy is associated with several limitations (7,8). Firstly, the clinical effect produced by BTX is temporary and repeated injections are required approximately every 3 months. Secondly, there is a delay in the onset of benefits provided by BTX injections; this delay results in a sinusoidal symptom curve where SD is optimally controlled for only 30% of a treatment cycle and patients' spasms return prior to the next injection cycle. Furthermore, the injections are very painful and some patients develop antibodies to BTX (7,8). Oral medications used in dystonia, such as anticholinergics, benzodiazepines, and baclofen, provide minimal relief and have numerous side effects at the doses required to influence a patient's voice. Thus, on basis of these limitations, we set out to explore new and innovative strategies to treat SD and provide patients with long-term benefit.

Deep Brain Stimulation (DBS) is a neurosurgical procedure that involves the implantation of electrodes to deliver electrical stimuli to specific brain regions (Figure 1). It is the gold-standard surgical treatment for other movement disorders such as Parkinson's disease and essential tremor (ET). During a DBS procedure, an electrode is inserted very precisely into the brain that is linked to a brain pacemaker implanted in the chest or abdominal wall. When the pacemaker is switched on, a very small electric current passes into the brain, blocking the damaging signals that cause the condition.

## ***Clinical Motivation***

Our team recently studied a small cohort of patients with LD and concurrent ET who underwent DBS for their ET. We found that these patients tremendously improved in their voice as a result of DBS. Scattered case reports are present in the literature of thalamic DBS improving voice in LD and concurrent ET. Based on our recent study and others elucidating the neural circuitry of LD, we are hoping to initiate a Phase 1 DBS trial in pure LD patients (those without essential tremor). This trial will be of international significance, span multiple specialties, and potentially revolutionize the standard of care for these patients.

## **Background**

In essential tremor, the ventralis intermedius (Vim) nucleus of the thalamus is the most common target for deep brain stimulation (DBS) and provides good to excellent results in the majority of patients. Some essential tremor patients also present with laryngeal dystonia (LD), a dystonic movement disorder of the laryngeal muscles. Multiple reports, including ours, have showed that Vim DBS for essential tremor and coincident LD improves voice. Previous reports from the Baylor College of Medicine found that unilateral ViM in essential tremor and coincident LD patients tremendously improved in voice. Furthermore, leaders in the field otolaryngology and speech-language pathology have expressed that the central neurological abnormality observed in LD must be treated, rather than treat the disorder at neuromuscular level (as done with BTX).

[figure not shown]
## **Hypothesis**

The ventral intermediate nucleus (Vim) of the motor thalamus receives somatosensory input from the cerebello-thalamic circuit (1-2,9). This circuit is desynchronized in LD as previous studies have shown that the Vim is involved in the motor control of laryngeal musculature (1,9). We believe that neuromodulation of this cerebellar circuit at the Vim will lead to significant vocal improvement in LD patients. We recently targeted the Vim for patients with coincident essential tremor and LD. We found that patients significantly improved in voice,

neurological, and quality of life outcomes; this publication is currently under preparation.

### Study Design

To investigate our hypothesis, we will conduct a prospective, randomized, double-blinded, crossover Phase 1 DBS trial in LD patients. Patients will be randomized to either active or sham-stimulation for 3 months, crossed-over, and conclude with open-label treatment for 6 months. Patient and assessors will be blinded to treatment allocation. Below is a graphical illustration of trial.

Previous Phase 1 trials for new indications of DBS have recruited N=6 patients. We plan to also recruit N=6 patients for this trial from the Pacific Voice Clinic. We will use a computer-generated 1:1 pairwised randomization sequence when the patients are enrolled into the trial, so that similar numbers of patients are recruited to each study group. Patients will be evaluated in a double-blinded manner for their voice and voice-related quality of life. Patients and rating clinicians will be masked to treatment allocation; an unmasked clinician will be responsible for programming the stimulation.

DBS stimulation parameters will be chosen based on standard programming guidelines. Primary endpoints will assess: (1) patient improvement in SD using the Unified Spasmodic Dysphonia Rating Scale (2) assess patient quality of life using the Voice-Related Quality of Life. Patients will also be asked their subjective assessment of each of the settings. [name] will be administering these scales.

We also will acquire two advanced neuroimaging scans: PET and DTI. The former will allow us to monitor neural network wide changes as a result of DBS. DTI will allow us to determine which white matter tracts are being activated as a result of this surgery. Once pilot\* testing of the PET protocol is completed, patients enrolled in this trial will be asked to obtain a PET scan at end of the 3-month mark and at the 6-month mark (see trial timeline above). DTI scan will only be required pre-operatively. The neuroimaging arm of our surgical trial will add considerable scientific rigour to our trial and helps us further elucidating the neurobiology of this disease.

At the Vancouver General Hospital (VGH), we have a 17-year experience with Deep Brain Stimulation Surgery. As of 2012, we have performed over 400 of these operations including DBS stimulator programming.

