***Un-randomization:***

In the case of an adverse or unanticipated event during this surgical trial, the patients will be un-randomized completely turned off. However, based on the literature and our 15-year experience, we expect all patients to experience at least some benefit (even if minimal to none) rather than deteriorating.

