**Organization**

At the Surgical Centre for Movement Disorders at Vancouver General Hospital, we have a 15-year experience with DBS surgery and programming for movement disorders. Patients eligible for this study will be all patients who have already underwent or who will be undergoing thalamic DBS surgery to ameliorate their essential tremor. Patients will be tracked through [name] clinic and given a research identification number. After enrollment, they will be followed-up by [name] and programming will begin one-month after surgery. Data will be burned onto a CD using only their research identification number. This data will then be analyzed to determine if there is an improvement in the patient’s spasmodic dysphonia symptoms and quality of life. The results will be published in a peer-reviewed journal with no reference to individual patients.

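### Allocation is drawn at enrolment but stimulation starts a month after surgery, so a patient lost in between uses up a sequence slot; drawing at first activation avoids this

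*Combined protocol and SAP*

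**What the plan says.** The sample size is six: "We plan to also recruit N=6 patients for this trial from the Pacific Voice Clinic". The Study Design section uses a "computer-generated 1:1 pairwised randomization sequence when the patients are enrolled into the trial", with the aim "so that similar numbers of patients are recruited to each study group". The word pairwised is not defined; blocks of two is the natural reading. What is allocated is a whole order of treatment: "Patients will be randomized to either active or sham-stimulation for 3 months, crossed-over, and conclude with open-label treatment for 6 months".

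On masking, "Patients and rating clinicians will be masked to treatment allocation", and "an unmasked clinician will be responsible for programming the stimulation". In the Organization section, follow-up comes after enrolment and "programming will begin one-month after surgery". The Un-randomization section says that after an adverse or unanticipated event "the patients will be un-randomized completely turned off".

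The Statistics section plans a repeated measures ANOVA over baseline, off and on stimulation, and an unpaired t test of the on-minus-off difference between sequences. The plan does not say who holds the list, whether the pairing is kept from masked staff, or whether a patient lost before activation is replaced and from which slot.

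**The concern.** For a patient enrolled before surgery, an operation and a month lie between the draw and the first day on which the allocation matters. Anyone who withdraws or is excluded in that interval contributes nothing to the blinded periods but has taken a slot. The list then balances enrolled patients, while the analysis needs balance among activated patients. With only three patients per sequence, one or two wasted slots can defeat the stated aim of similar numbers. At stake are how evenly the two period orders are represented and how informative the between-sequence t test is.

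**Working it through.** **Inputs.** From the plan: N = 6, 1:1 in pairs (read as blocks of two), allocation at enrolment, programming one month after surgery. The plan gives no rate of loss before activation, so 5%, 10% and 20% per patient are assumptions.

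**The plan's own balance.** Three blocks of two give 2 × 2 × 2 = 8 possible lists, and all of them are 3:3. The design meets its aim if all six are activated.

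**Losses after a draw at enrolment, no replacement** (each patient equally likely to be lost):
- One lost: always 3:2.
- Two lost: there are 15 possible pairs of patients. In 3 × 3 = 9 the two have opposite sequences, leaving 2:2 (9/15 = 0.6). In 6 they have the same sequence, leaving 3:1 (6/15 = 0.4).

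**One loss, replaced from the next slot.** The seventh slot opens a new pair, so it matches the lost patient's sequence with probability 0.5. The result is 3:3 in half the cases and 4:2 in the other half. If the lost patient may be any of the seven enrolled, including the seventh, the chance of 3:3 is 1/7 + (6/7) × 0.5 = 0.571.

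**Draw at first activation, pairs kept.** Slots are used only by activated patients: six give 3:3, five give 3:2, four give 2:2, each with certainty.

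**Effect on the sequence t test.** The variance of the difference between sequences is proportional to 1/n1 + 1/n2, with n1 + n2 − 2 degrees of freedom:

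| Split | 1/n1 + 1/n2 | df |
|---|---|---|
| 3:3 | 0.667 | 4 |
| 4:2 | 0.750 | 4 |
| 3:2 | 0.833 | 3 |
| 2:2 | 1.000 | 2 |
| 3:1 | 1.333 | 2 |

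At the same number activated, the avoidable penalty is 0.750/0.667 = 1.125 for six patients and 1.333/1.000 = 1.333 for four. For five there is none.

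**How often it would matter, with assumed loss rate q.** P(at least one loss) = 1 − (1 − q)^6. P(exactly two) = 15 q²(1 − q)^4. Multiplying the latter by 0.4 gives the chance of an avoidable 3:1 without replacement:

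| q | At least one lost | Exactly two lost | 3:1 |
|---|---|---|---|
| 5% | 0.265 | 0.031 | 0.012 |
| 10% | 0.469 | 0.098 | 0.039 |
| 20% | 0.738 | 0.246 | 0.098 |

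**The case against.** The best defence is that the timing hardly matters here. The on/off comparison is within patient, the Statistics section states no period term, and the sequence t test is a supporting check. The commonest single problem, one unreplaced loss, gives 3:2 whenever the draw is made. The Organization section also admits patients who have already had thalamic surgery, for whom the interval may be short. (That section's essential tremor population must itself be reconciled with Clinical Motivation, which describes patients without essential tremor.) All of this stands and limits the size of the point. It does not remove it, because the later draw costs almost nothing and serves the plan's own aim.

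A reader might infer more, in two ways that the documents do not support.

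*That pairing is itself a defect and must give way to one 3:3 list of six.* In blocks of two, the second allocation of each pair is fixed by the first, so 3 of 6 are certain to someone who knows the earlier ones. With one list the average is 1.5. The best guesser's expected score, however, falls only from 4.5 to 4.1 of six. After one code break, expected correct guesses over the other five patients are the same: 1 + 4 × 0.5 = 3.0 with pairs and 5 × 0.6 = 3.0 with one list. Pairs concentrate the leak on one patient; one list spreads it over five. If only four patients are activated, one list gives 3:1 in 40% of cases and pairs never do. Nor does the Un-randomization section say that raters or other patients are told the code. The index patient is exposed under any scheme, so the additional exposure from pairing is one patient of six, and only to someone who is told the code and knows the pairing.

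*That a lost slot raises the variance of the on/off effect by 25%.* The ratio is (1/3 + 1/2)/(1/3 + 1/3) = 1.25, but going from six patients to five accounts for (1/5)/(1/6) = 1.20. Imbalance adds only about 4%, and that assumes a period-adjusted analysis which the Statistics section does not state.

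**Conclusion.** The point holds as one about timing and is minor. For patients enrolled before surgery, drawing at enrolment lets a loss before activation consume a slot. The avoidable harm is a 3:1 split in 40% of cases with two unreplaced losses, or 4:2 in about half of cases with one loss replaced from the next slot. It falls mainly on period balance and the sequence t test. These probabilities assume blocks of two and losses unrelated to sequence. How often the situation arises depends on a loss rate that the plan does not give. The finding does not require the sponsor to abandon pairs, and it does not show that masking fails in a second patient.

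**What to change.** In Study Design, replace allocation at enrolment with wording such as: each patient's sequence is taken from the next unused position on the computer-generated 1:1 list on the day of first activation; the list is held only by the unmasked programming clinician, and the pairing is not disclosed to patients or raters. State also what pairwised means. Pairs may be kept.

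The cost is one sentence and one procedural step: the programming clinician must draw the allocation at the first programming visit. Sample size, visits and treatment do not change. The change does not help with patients lost after activation, and five activated patients will still be 3:2.

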**Statistics**

We will compare the primary (Unified Spasmodic Dysphonia Rating Scale) and secondary endpoints (Quality of Life) at baseline, for the off- stimulation period and the on-stimulation period, with repeated measures ANOVA. For the endpoints in which a significant effect of timepoint ( $p < 0.05$ ) was identified, pairwise comparisons will be performed between each of the three timepoints (baseline *versus* off stimulation, baseline *versus* on stimulation, and on stimulation *versus* off stimulation) and a Bonferroni-corrected p values will be completed.

We will also compare the effect of randomisation sequence on the difference in USDRS scores between the on-stimulation and off-stimulation periods in the blinded phase of the trial using an unpaired *t* test.

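### Quality of life is primary in one section and secondary in another, and the Statistics section does not name on versus off stimulation as the deciding contrast

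*Combined protocol and SAP*

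**What the plan says.** **Endpoint tier.** Study Design: "Primary endpoints will assess: (1) patient improvement in SD using the Unified Spasmodic Dysphonia Rating Scale (2) assess patient quality of life", with V-RQOL as the quality-of-life scale. Statistics: "We will compare the primary (Unified Spasmodic Dysphonia Rating Scale) and secondary endpoints (Quality of Life) at baseline". USDRS is primary in both sections, so only the standing of quality of life is in dispute. Both are current text, and neither is said to take precedence.

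**Comparison.** Statistics applies a repeated measures ANOVA to three conditions: baseline, off stimulation and on stimulation. It continues "For the endpoints in which a significant effect of timepoint" is found at p < 0.05, "pairwise comparisons will be performed between each of the three timepoints", with Bonferroni correction. The three pairs are baseline versus off, baseline versus on, and on versus off, and none is ranked above the others. A separate unpaired t test asks whether randomization sequence affects the "difference in USDRS scores between the on-stimulation and off-stimulation periods in the blinded phase of the trial". That test concerns order, not treatment.

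**Design.** "Patients will be randomized to either active or sham-stimulation for 3 months, crossed-over", and "Patient and assessors will be blinded to treatment allocation". Six patients are planned, followed after the crossover by six months of open-label treatment.

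**Aim.** The Hypothesis section expects the voice to improve with stimulation but does not say relative to what. The Organization section says "This data will then be analyzed to determine if there is an improvement in the" patients' symptoms and quality of life, again with no comparator.

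**The concern.** The two sections give different answers to how many primary endpoints there are. A reader of the results could not tell whether a V-RQOL finding is a main result or a supporting one.

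The contrast matters more. Baseline is not a randomized condition. Surgery, placebo response or the passage of time can move both blinded periods away from it by the same amount. The ANOVA and the on-versus-baseline pair both respond to such a shift; on versus off does not. Because the plan does not say which result answers the hypothesis, a significant ANOVA or on-versus-baseline pair could be presented as the trial's finding even if active and sham stimulation give the same voice scores. Moving V-RQOL to secondary would not cure this, because the same ambiguity exists within USDRS.

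**Working it through.** **Inputs from the documents.** N = 6 (Study Design); three conditions, ANOVA at 0.05, three pairs with Bonferroni correction (Statistics). The per-pair level is 0.05/3 = 0.0167. N = 6 rests on the size of earlier Phase 1 trials. No effect size, SD or power is given, so that figure cannot be re-derived.

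**Assumptions.** Normal data, equal variances, independent errors at each timepoint (SD 1), two-sided pairwise tests, and a correlation between endpoints of 0, 0.5 or 0.8. The shifts from baseline and the effect sizes below are also assumed, since the documents state none.

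**Critical values.** F(2,10) at 0.05 = 4.103. |t| with 5 df = 3.534 at 0.05/3 and 2.571 at 0.05. |t| with 4 df = 2.776 at 0.05.

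**1. No on-off effect, both periods shifted from baseline by δ SD.** The ANOVA noncentrality is 6 × Σ(μ − mean μ)² = 6 × (2/3)δ² = 4δ², that is 4, 16 and 36 for δ = 1, 2, 3. The noncentral F distribution gives the first row; the other rows are simulated, with each pair counted only after a significant ANOVA.

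| USDRS only | δ = 1 | δ = 2 | δ = 3 |
|---|---|---|---|
| ANOVA significant | 32% | 87% | 99.7% |
| On vs baseline significant at 0.05/3 | 11% | 53% | 89% |
| On vs baseline significant, on vs off not | 11% | 52% | 88% |
| On vs off falsely significant at 0.05/3 | 1.4% | 1.6–1.7% | 1.7% |

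With no shift, the last row is 1.0%.

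**2. Effect of the tier conflict.** If a significant ANOVA on either endpoint counted as success, two independent endpoints with no effect at all would give 1 − 0.95² = 9.75%, falling to about 8.2% at correlation 0.8. The plan goes on to corrected pairs. A false on-off result on either endpoint, after the ANOVA gate and 0.05/3, occurs in about 1.7% to 1.9% of trials with no shift. With a shift it stays at or below about 3.4% (two independent endpoints at 1.7% each: 1 − 0.983² = 3.4%).

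**3. Power of possible deciding tests of on versus off.** Let d be the true difference in SDs of the paired difference; the noncentrality is d√6, which is 3.67 at d = 1.5.

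- Gate and 0.05/3: about 59% at d = 1.5, with 1.0% to 1.7% false positives.
- Simple paired test at 0.05, 5 df: 83% at d = 1.5 and 5% false positives, if there is no period effect. With three patients per sequence and an assumed period difference of 1 within-timepoint SD, these become 66% and 1.9%. At a 2 SD period difference, power is 26%.
- Period-adjusted test at 0.05, 4 df (average of the two sequence means, pooled within-sequence SD): 78% and 5% whatever the period difference, assuming no carryover.

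**The case against.** The strongest reply is that the plan already points to on versus off. The hypothesis is to be investigated through a randomized, blinded crossover. The Statistics section lists the on-off pair, and it uses the on-off USDRS difference for the sequence check. All three pairs are run together, so a baseline result would appear beside the on-off result. This stands as a fair reading of intent: on versus off is in the plan, and a reader who inferred that it was missing would be wrong. But the intent is implied, not stated.

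A reader might also infer that the plan's active-versus-sham test has a false-positive rate of 87% or more. It does not. Where baseline truly differs, a significant ANOVA correctly detects a difference between timepoints. The error would lie in reading that as an effect of stimulation. The on-off pair itself is conservative.

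A third tempting reading is that the tier conflict doubles the error rate to 9.75%. That needs an ANOVA alone, on either endpoint, to count as success. Study Design does not say this; if both endpoints were required, the rate with no effect would be at most 5%.

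Finally, this is a six-patient Phase 1 trial with no stated success threshold. That limits the weight of the point. Yet the Significance section gives efficacy as the aim, so which result counts still matters.

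**Conclusion.** The point holds in two parts. The two sections contradict each other on the tier of quality of life, and the documents do not settle which is in error. The Statistics section also leaves its only randomized, blinded contrast as one of three unranked pairs behind a three-condition ANOVA.

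The second part carries the weight. Under the assumed shifts, a baseline difference without an on-off difference would be available to report in 11% to 88% of trials. These figures illustrate a mechanism; the conclusion rests on the text and does not depend on them. The tier conflict by itself has little effect on the active-versus-sham claim. This should be fixed, but it does not invalidate the design or the on-off test.

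**What to change.** Before unblinding:

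1. Bring Study Design and Statistics to one endpoint hierarchy. The simplest is USDRS as the single primary and V-RQOL as secondary, because Statistics is the analysis text and USDRS is primary in both. The cost is that V-RQOL loses primary status.
2. In Statistics, name on versus off on USDRS in the blinded phase as the deciding contrast. Make the ANOVA, both baseline comparisons and all V-RQOL results supportive.
3. State the level of that contrast in advance. This is a separate trade-off, and naming the contrast does not force a change of test. Keeping the ANOVA gate and 0.05/3 is valid but conservative, with about 59% power at an assumed 1.5 SD. If one two-sided 0.05 test is used instead, adjust it for period: about 78% power at 1.5 SD, and 5% rather than 1.0% to 1.7% false positives, given no carryover. The simple paired test should not be adopted on the strength of its 83%, which requires no period effect.

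The change is a short amendment to two sections, with no new patients or data.
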